The primary outcome measure is change in Magnetic resonance imaging (MRI) based FCA Severity Score (FCASS) from baseline to 1 month, compared between the two study arms. In addition, the study comprises various clinical and imaging-based information as well as analyses of adverse reactions.

Discussion

This will be one of the first prospective treatment trials in the field of pediatric stroke. The preparation for the study has already impacted stroke care of children worldwide through development of international collaborative trial networks and standardized neuroimaging based vascular scoring system.

PASTA (Pediatric Arteriopathy Steroid Aspirin) trial

Pediatr Stroke. 2023;6: 21-42

www.pediatricstrokejournal.com

pediatric stroke

Study Protocol

PASTA (Pediatric Arteriopathy Steroid Aspirin) trial

Pediatr Stroke. 2023;6: 21-42

www.pediatricstrokejournal.com

Introduction and rationale

Due to the suspected inflammatory cause of focal arteriopathy of the inflammatory type (FCA-i), it is increasingly treated with steroids - so far without firm evidence.¹⁻⁴

In more than half of children with arterial ischemic stroke (AIS), arteriopathy is the underlying cause.⁵ This is further subdivided into a small vessel as well as a large vessel bilateral and unilateral arteriopathy depending on the distribution of the affected vessels. The term focal cerebral arteriopathy (FCA) is often used synonymously with the term unilateral arteriopathy in the literature. When the term is used in this sense, no distinction is made as to what is the cause of this arteriopathy.⁶

In addition, the term FCA is used much more specifically for a subtype of unilateral arteriopathy^{5,7}: This is a mostly unilateral monophasic disease of the cerebral arteries. Although the exact pathophysiology for the latter remains unknown, there is increasing evidence of a transmural inflammatory process of the vessel wall (see Fig. 1).⁸⁻¹⁰ This has led to the additional designation of the term "FCA of the inflammatory type" (FCA-i).⁹ Which distinguishes this from other forms of unilateral arteriopathy, such as moyamoya and dissection. The question of the extent to which FCA-i can also be present bilaterally is the subject of current research.

According to a retrospective Australian-Swiss study, steroid treatment in FCA-i is associated with

PASTA (Pediatric Arteriopathy Steroid Aspirin) trial

pediatric stroke

Study Protocol

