a significantly better neurologic outcome¹ and an uncontrolled case series, showed that steroid treatment reduced vessel wall enhancement.¹⁰ In contrast, it has also been postulated that infectious mechanisms may play a role in the pathophysiology of FCA-i, and concerns have been raised about possible adverse effects of steroid treatment on these mechanisms.^{11,12} The mechanism has best been studied for varicella related FCA-i: After systematic infection varicella virus remains in ganglions (“sleeping”). By reactivation there is a neuronal transport of the virus, followed by inflammatory process in the vessel wall.¹³ For other disease-causing microorganisms, the pathophysiology is less clear, but likely similar. Reflective of the resulting uncertainty and equipoise, a Delphi survey of pediatric stroke specialists identified a steroid trial in children with FCA-i as the most important and feasible trial in this research field.⁴

To assess the severity of stenosis and the course of FCA-i in a standardized manner, the Focal Cerebral Arteriopathy Severity Score (FCASS) was developed in 2018. It is calculated based on the degree of arterial stenosis in MR, CT or conventional angiography in five cerebral arterial segments. Consistent with the natural history of FCA-i, FCASS increases in the first months of the disease and then decreases thereafter. The score was shown to be reliable and to correlate with long-term outcome as well as stroke volume.^{12,14}

The objectives of this study are to evaluate if early anti-inflammatory treatment may influence

PASTA (Pediatric Arteriopathy Steroid Aspirin) trial

pediatric stroke

Study Protocol

the course of arteriopathy, improve clinical outcomes, and prevent stroke recurrence in children with FCA-i.

The primary hypothesis is, that children with FCA-i treated with a course of high dose methylprednisolone/prednisolone will show greater improvement of focal stenosis and arteriopathy as measured by FCASS.

Methods

Design

This is a PROBE-study, comparing a high-dose course of intravenous methylprednisolone/oral prednisolone plus standard care versus standard care alone in children with FCA-i. The study will be conducted in 27 centers in Australia, Austria, France, Germany, Switzerland, and the United Kingdom.

Recruitment of participants is planned to occur over a period of 36 months. The data collection is shown in Fig. 2.

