Probabilistic minimization will be used, accounting for the following stratification factors: age (6 months through 5 years, 6 years through 11 years, 12 years to under 18 years) and pediatric National Institute of Health Stroke Scale (Ped-NIHSS; < 7, 7 to 12, >12).

Trial participants and local data collectors will not be blinded, as steroid treatment causes obvious clinical signs and symptoms. Imaging outcomes will be centrally assessed by blinded neuroradiologists.

The telephone-interview-based assessments of RRQ (Recurrence and Recovery Questionnaire), mRS (modified Rankin Scale) and VABS (Vineland Adaptive Behavior Scales) will be performed

PASTA (Pediatric Arteriopathy Steroid Aspirin) trial

pediatric stroke

Study Protocol

blinded centrally for all study participants.

Intervention

Participants in both study arms will be treated based on standard care, including antithrombotic treatment with daily oral aspirin (3-5mg/kg/day, maximum 150mg/day). The hyperacute treatment (including intravenous thrombolysis and endovascular thrombectomy) may be performed according to local protocol. Start with any type of anticoagulation is possible and should be done as by local protocol. Switch or start of aspirin is mandatory at latest at inclusion. Suggestions (see supplementary) for standard care are given to the sites but noncompliance is not a deviation to the protocol. These suggestions have been discussed and approved by the international steering committee of the PASTA trial (see Appendix 1).

In addition, participants in the treatment arm will receive 3 days of intravenous methylprednisolone 30mg/kg/day (max. 1000mg/dose) in one daily dose. This is followed by therapy with oral prednisolone 1 mg/kg/day (max. 40mg/day) for 2 weeks and 0.5mg/kg/day (max. 20mg/day) for another 2 weeks.

Outcomes

The Primary Outcome is the change in FCASS from baseline examination to 1 month. In

PASTA (Pediatric Arteriopathy Steroid Aspirin) trial

Pediatr Stroke. 2023;6: 21-42

www.pediatricstrokejournal.com

addition, various imaging data, clinical and safety outcomes will be assessed (see table 2).

Primary Outcome

● Change in FCASS from baseline to 1 month
Secondary Outcomes
Imaging

● Change in FCASS from baseline to 6 months● Volume of stroke (in FLAIR and DWI-sequences) at baseline, 1, 3 and 6 months by modified pediatric ASPECTS● Residual arteriopathy at 6 months by FCASS
Clinical

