Central data monitoring and validation will be performed according to a separate monitoring plan continuously for each site. This will include regular verification of the completeness, accuracy, and plausibility of the entered data and to query the site and follow up anything requiring clarification. No interim analyses are planned and no safety stopping points are defined.

Sample size estimates

For 13 patients of a retrospective study the standard deviation of the change in FCASS from baseline to maximum severity of arteriopathy was 2.8.¹⁴ Based on this standard deviation and a two-sample means test, 64 patients (32 in each group) are required to detect a difference of 2.0 with a power of 80% at a two-sided alpha-level of 0.05.

PASTA (Pediatric Arteriopathy Steroid Aspirin) trial

pediatric stroke

Study Protocol

To account for dropouts (8%), we will enlarge the sample size to 70 patients (35 in each group).

Statistical Analyses

The primary analysis will follow the intention-to-treat (ITT) principle. The primary outcome and secondary continuous variable outcomes that are measured multiple times during follow-up will be assessed in a repeated-measure, mixed-effects linear model.

Neurocognitive outcomes measured at 1 year will be analyzed using a mixed-effects linear model, binary outcomes (recovery, residual arteriopathy) will be assessed using generalized linear mixed-effects models, Time-to-event outcomes (stroke recurrence, infection requiring hospitalization, progressive arteriopathy) will be analyzed using Cox-regression, accounting for the stratification factors used at randomization (country and baseline FCASS).

We will perform a subgroup analysis according to baseline FCASS (<8 vs ≥8), accompanied by an appropriate test of interaction. Moreover, we will test whether the baseline FCASS (used continuously) has an influence on the association between steroid treatment and modified ASPECT score, i.e. whether there is effect modification (interaction).

Scores measured repeatedly over time (FCASS, mRS, PSOM, VABS, modified pediatric ASPECT) might be considered as categories. Patients may shift from category to category several times

PASTA (Pediatric Arteriopathy Steroid Aspirin) trial

pediatric stroke

Study Protocol

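### The primary mixed model names neither baseline FCASS nor the minimization factors, and the protocol's only adjustment clause lists different randomization factors from those it minimizes on

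*Protocol*

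**What the plan says.** **Endpoint.** The Outcomes section states: "The Primary Outcome is the change in FCASS from baseline examination to 1 month". The abstract describes the same change "from baseline to 1 month, compared between the two study arms". Change to 6 months is listed separately as a secondary outcome.

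**Primary model.** Under Statistical Analyses, "The primary analysis will follow the intention-to-treat (ITT) principle". The next sentence puts the primary outcome and the repeated continuous secondary outcomes under one method: these "outcomes that are measured multiple times during follow-up will be assessed in a repeated-measure, mixed-effects linear model". It gives no covariate, visit term or contrast.

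**Adjustment.** The sentence after that covers neurocognitive, binary and time-to-event outcomes. It ends, after Cox regression, with "accounting for the stratification factors used at randomization (country and baseline FCASS" and a closing bracket.

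**Randomization.** The section Randomization and blinding reads: "Probabilistic minimization will be used, accounting for the following stratification factors: age (6 months through 5 years", followed by two further age bands and three Ped-NIHSS bands. Neither country nor baseline FCASS appears there.

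**Other uses of baseline FCASS.** Apart from the adjustment clause, it serves only for subgroup and effect-modification analyses, for example: "We will perform a subgroup analysis according to baseline FCASS (<8 vs ≥8), accompanied by an appropriate test of interaction".

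**The concern.** The protocol does not simply leave adjustment to a later document. It takes the subject up and contradicts itself. The clause can be read in two ways:

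- **It belongs to the Cox models, or at most to its own sentence.** This is the natural reading. The primary model then has no stated covariate.
- **It reaches back to the primary model.** The named covariates are then country and baseline FCASS, and age and Ped-NIHSS are still missing.

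Either way, the two factors that the allocation is built to balance appear in no stated analysis. Minimization makes the arms more alike on these factors than simple randomization would. If the factors predict the outcome, an analysis that ignores them still counts their variation as noise, so its standard error tends to be too large. If the randomization section is the correct one, baseline FCASS is not balanced by design, and chance imbalance is then a practical matter with 35 children per arm.

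At stake are precision in a small trial planned at 80% power, and a covariate set for the primary test that the protocol leaves open.

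**Working it through.** **1. The plan's own figure.** Inputs from Sample size estimates: difference 2.0, SD 2.8, two-sided alpha 0.05, power 80%, 1:1 allocation.

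- Two-sample t-test (noncentral t): 31.76, so 32 per arm and 64 in total. Power at 32 per arm is 80.3%.
- Dropout of 8%: 64 / 0.92 = 69.6, so 70.

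Both stated figures reproduce with no covariate. The planned power does not rely on adjustment.

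**2. The two lists of factors side by side.**

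| Place | Factors given as used at randomization |
|---|---|
| Randomization and blinding | age (3 bands), Ped-NIHSS (3 bands) |
| Statistical Analyses, adjustment clause | country, baseline FCASS |

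The lists share no factor.

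**3. What baseline adjustment could change.** The protocol gives no correlation between baseline and 1-month FCASS, so the values below are assumptions. Set the baseline SD to 1, the 1-month SD to k and their correlation to rho. Then:

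- variance of the change = 1 + k² − 2·k·rho
- covariance of change with baseline = k·rho − 1
- r = (k·rho − 1) / √(1 + k² − 2·k·rho)
- residual variance after adjustment = (1 − r²) × variance of the change

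With k = 1 the factor 1 − r² simplifies to (1 + rho)/2. The residual SD is 2.8 × √factor, and power is for a t-test at 32 per arm:

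| k | rho | Factor | Residual SD | Power | Equivalent unadjusted N (64 / factor) |
|---|---|---|---|---|---|
| no adjustment | – | 1 | 2.80 | 80.3% | 64 |
| 1 | 0.3 | 0.65 | 2.26 | 93.7% | 98 |
| 1 | 0.5 | 0.75 | 2.42 | 90.1% | 85 |
| 1 | 0.7 | 0.85 | 2.58 | 86.2% | 75 |
| 1 | 0.9 | 0.95 | 2.73 | 82.3% | 67 |
| 1.4 | 0.7 | 0.9996 | 2.80 | 80.3% | 64 |

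In the last row the covariance is 0.7 × 1.4 − 1 = −0.02 and the variance of the change is 1 + 1.96 − 1.96 = 1.00, so r = −0.02 and the gain vanishes. Unequal variances are plausible, because the Introduction says that "FCASS increases in the first months of the disease and then decreases thereafter".

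**4. The same check without assuming equal variances.** Let r be the correlation of the 1-month change with all added covariates together, so that the residual SD is 2.8 × √(1 − r²). Power is 80.3% at r = 0, 81.9% at 0.2, 83.9% at 0.3, 86.6% at 0.4 and 90.1% at 0.5.

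**5. Two limits on these figures.** The SD of 2.8 comes from 13 patients and describes change to maximum severity, not to 1 month. The power values also ignore the degrees of freedom spent on covariates. Baseline (1), age (2) and Ped-NIHSS (2) take the error degrees of freedom from 62 to 57, which lowers power by about 0.1 percentage point.

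**The case against.** **Covariates are ordinary analysis-plan content.** A journal-length protocol often leaves covariates, time coding and the reported contrast to the statistical analysis plan. Nothing here excludes baseline FCASS, age or Ped-NIHSS, and a repeated-measures model with baseline as one of the responses would also use the baseline information. This stands against any claim that precision is being thrown away: the text does not secure it, which is different. It does not answer the conflict between the two lists of factors, which the protocol itself states.

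**Nothing is invalid.** In a randomized comparison, chance imbalance and regression to the mean do not bias the contrast of change scores, and 64/70 is right without adjustment. This stands in full.

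**The gain may be nil.** This also stands. It is about 2 percentage points at rho 0.9 and essentially zero in the unequal-variance case.

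**A stronger reading to avoid.** Because one modelling sentence covers several visits and FCASS rises before it falls, a reader might infer that the primary test is an arm effect pooled over 1 and 6 months, which could understate the 1-month effect. The protocol does not support this. The abstract and the Outcomes section fix the comparison at 1 month, 6 months is a separate secondary outcome, and no pooled or linear-time model is described. Any figure for such dilution would need invented effects at both visits. What remains is that the model sentence does not say which term is the primary test.

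**Conclusion.** The point holds as an internal contradiction plus an improvement that needs no new data. The firm part is textual: two sections give non-overlapping lists of randomization factors, and age and Ped-NIHSS appear in no stated analysis whichever way the adjustment clause is read.

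The size is uncertain. Across the assumed correlations and variance ratios, adjustment would take power at 32 per arm from 80% to between about 80% and 94%. The upper end needs equal variances and a baseline-to-1-month correlation as low as 0.3. A reader might infer that the trial is underpowered or its analysis invalid. Neither follows, since the sample size reproduces and an unadjusted analysis would be valid.

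**What to change.** 1. Reconcile Randomization and blinding with Statistical Analyses, so that both name the factors actually used in the minimization.
2. Say which analyses the adjustment clause covers.
3. State the primary model: FCASS change at the scheduled 1- and 6-month visits; fixed effects for arm, categorical visit, arm-by-visit, baseline FCASS (continuous), age group and Ped-NIHSS category; child as the repeated unit.
4. Name the arm contrast at 1 month as the primary test, which matches the abstract and the Outcomes section.

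If the reconciliation shows that other factors were used in the minimization, those belong in the model too. Restricting the model to scheduled visits also settles whether scores from the 3-month MRI, done only when clinically indicated, enter the primary analysis.

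The cost is wording in the protocol, and in the analysis plan if it does not already say this. No new data or visits are needed, and the sample size does not change. The covariates should be fixed before outcome data are compared by arm.

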
● Functional impairment outcome by PSOM at 1, 3, 6 and 12 months● Recovery by RRQ at 1, 3, 6, and 12 months● Degree of disability or dependence by mRS at 1, 3, 6, and 12 months● Adaptive function by VABS at 6 and 12 months● For children aged >2 years, quality of life at 12 months, by PSQLM● Neurocognitive outcome at 12 months
Mixed clinical/imaging

● Stroke recurrence assessed at 1, 6 and 12 months defined as:
- New focal neurological deficit(s) or- Worsening of the neurological deficits by > 4 pedNIHSS points lasting for more than 24 hours with new or increased diffusion restriction in the corresponding vascular territory, or- New areas of clinically silent infarction, remote from the initial infarct
Safety Outcomes

● Late diagnosis of progressive large to medium vessel childhood primary angiitis of the CNS● Adverse events (abnormal blood pressure, abnormal blood glucose, behavioral problems, infections, gastrointestinal irritation, electrolyte abnormalities requiring

PASTA (Pediatric Arteriopathy Steroid Aspirin) trial

intervention or weight gain)

- Infectious episodes requiring hospitalization
- Serious adverse events related to the study intervention requiring medical intervention

Table 2: Outcome Measures. FCASS: Focal cerebral arteriopathy severity score; ASPECTS: Alberta stroke program early CT score, PSOM: Pediatric Stroke Outcome Measure; RRQ: Recurrence and Recovery Questionnaire; mRS: modified Rankin Scale; VABS: Vineland Adaptive Behavior Scale; PSQLM: Pediatric Stroke Quality of Life Measure; ped NIHSS: pediatric National Institute of Health Stroke Scale.

Imaging Outcomes

Magnetic resonance imaging and angiography (MRI/MRA) will be performed at baseline, 1 and 6 months and, if clinically indicated at 3 months. The imaging protocol will comprise at least DWI/ADC, FLAIR, T2-weighted, time of flight (ToF) MR angiography and SWI sequences. At baseline neck vessel and vessel wall imaging should be considered. MRIs should be performed at 3 Tesla and without sedation or anesthesia if possible. All images will be assessed centrally by two independent neuroradiologists.

The degree of arterial stenosis at different time points is measured using FCASS in MRA.

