Stroke Volume is measured by modified pediatric ASPECTS, a semi quantitative imaging score in childhood stroke where each abnormal area is assigned one point. Higher scores represent greater volumes, with a maximum possible score of 30 (15 per hemisphere).^{15,16}

Clinical Outcomes

PASTA (Pediatric Arteriopathy Steroid Aspirin) trial

pediatric stroke

Study Protocol

The pedNIHSS, an adaptation of the adult NIHSS to the pediatric population, is used to assess the severity of stroke.¹⁷ The Pediatric Stroke Outcome Measure (PSOM), which is used to determine neurologic outcome, was developed, and validated specifically for pediatric stroke. It addresses pediatric specific domains such as development, behavior and cognition in addition to sensory-motor and language function.^{18,19} To improve quality of data for pedNIHSS and PSOM, explanatory videos were created for all investigators. These are available at (<https://www.pasta-trial.ch>).

By telephone, the modified Rankin Scale (mRS) is collected to determine disability or dependence and the Recurrence and Recovery Questionnaire (RRQ) to determine recovery and recurrence. In addition, the Vineland adaptive behavior scale (VABS) is collected to monitor behavior and cognitive abilities. The VABS and mRS are widely used tests, which are well validated.^{20,21} The RRQ was specifically developed and validated for pediatric stroke patients and addresses pediatric- specific problems of manifestation of stroke and also difficulties in reliable clinical examination.²²

At the end of follow-up, Quality of life is assessed using the Pediatric Stroke Quality of Life Measure (PSQLM)²³ and standardized neurocognitive testing (using either WISC-V or WPPSI-IV, depending on age) is performed. Within the framework of this examination, children over the

PASTA (Pediatric Arteriopathy Steroid Aspirin) trial

pediatric stroke

Study Protocol

age of 8 are additionally assessed for executive functions using subtests of the Delis-Kaplan Executive Function System (D-KEFS) and attention using Continuous performance task (CPT-III).

Data monitoring body

On site monitoring will be conducted at the first 5 sites that enroll a participant as soon as their first participant has reached the 30-day follow-up visit. Subsequent on-site and remote monitoring visits will be done randomly and by risk-based assessment.

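### Hospitalised infection is assigned a Cox model with no stated risk window; if one hazard ratio spans 12 months, an excess during the 31-day steroid course is diluted toward 1.

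*Protocol*

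**What the plan says.** The Safety Outcomes in Table 2 of the Protocol list "Infectious episodes requiring hospitalization". No assessment time or observation period is attached, whereas the clinical and recurrence outcomes in the same table carry theirs.

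Statistical Analyses gives the method: "Time-to-event outcomes (stroke recurrence, infection requiring hospitalization, progressive arteriopathy) will be analyzed using Cox-regression". The only modelling detail is the adjustment, "accounting for the stratification factors used at randomization (country and baseline FCASS"). No censoring time, period term or time-varying effect is mentioned.

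The Intervention section fixes the exposure in the experimental arm: "3 days of intravenous methylprednisolone 30mg/kg/day (max. 1000mg/dose) in one daily dose", followed by "oral prednisolone 1 mg/kg/day (max. 40mg/day) for 2 weeks and 0.5mg/kg/day (max. 20mg/day) for another 2 weeks".

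The length of follow-up has to be read from other outcomes, for example "Degree of disability or dependence by mRS at 1, 3, 6, and 12 months" in Table 2. Clinical Outcomes refers to the end of follow-up only for other measures: "At the end of follow-up, Quality of life is assessed".

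**The concern.** A Cox model with a single treatment term estimates one hazard ratio for the whole period analysed. Here the arms differ in steroid exposure for about one month and not after that. If steroids raise the risk of serious infection, the excess should fall mainly during and shortly after the course, so a constant hazard ratio is implausible by design. Later infections, about equally frequent in both arms, pull the fitted ratio toward 1. This happens even if every infection is captured and correctly classified.

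What is at stake is how a harm outcome is read. The predictable direction of the dilution is toward less apparent harm. The protocol also plans no interim analysis and no safety stopping points, so the comparison at the end of the trial carries the weight. A modest 12-month hazard ratio could be taken as reassurance about the treatment month, a question it does not answer.

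**Working it through.** **Inputs from the Protocol.** Exposure is 3 + 14 + 14 = 31 days (Intervention). With 365 days of follow-up, 365 − 31 = 334 days are off trial steroid, and 31/365 = 8.5% are on it. For group size, 64/(1 − 0.08) = 69.6, which reproduces the stated 70, or 35 per arm. The protocol gives no infection rate, event count or hazard ratio, so there is no infection figure to reproduce.

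**Assumptions.** On-treatment hazard ratio h = 3 or 5 for days 0–31, and 1 afterwards. Background hazard in days 0–31 is m times the later hazard, with m = 1, 4 or 10. Control 12-month risk is 2% to 20%. Follow-up is complete, and one constant hazard ratio is fitted over 12 months.

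**Step 1, approximation for rare events.** The fitted ratio is close to the ratio of cumulative hazards, (31·m·h + 334)/(31·m + 334).

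**Step 2, large-sample Cox estimate.** Solve for β: ∫[S_T λ_T − (S_T λ_T + S_C λ_C)·S_T e^β/(S_T e^β + S_C)] dt = 0, where S and λ are the survival and hazard functions in the steroid (T) and control (C) arms.

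| m | h | Step 1 | Step 2, control risk 2–20% |
|---|---|---|---|
| 1 | 3 | 427/365 = 1.17 | 1.17–1.19 |
| 1 | 5 | 489/365 = 1.34 | 1.34–1.38 |
| 4 | 3 | 706/458 = 1.54 | 1.55–1.60 |
| 4 | 5 | 954/458 = 2.08 | 2.09–2.21 |
| 10 | 3 | 1264/644 = 1.96 | 1.97–2.04 |
| 10 | 5 | 1884/644 = 2.93 | 2.94–3.10 |

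**Step 3, carry-over.** If the excess lasts two months (62 days) with a flat background, Step 1 gives (62·3 + 303)/365 = 1.34 and (62·5 + 303)/365 = 1.68. The Cox estimates are 1.35–1.38 and 1.70–1.76 for control risks of 5–20%. Dilution is smaller but remains.

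**Step 4, expected events and precision.** Take a flat background and 10% control risk over 12 months.
- Control risk to day 31: 1 − 0.9^(31/365) = 0.89%.
- Steroid-arm risk to day 31: for h = 3, 1 − 0.9^(93/365) = 2.65%; for h = 5, 1 − 0.9^(155/365) = 4.38%.
- Events to day 31, both arms: 35 × (0.0089 + 0.0265) = 1.2 for h = 3; 35 × (0.0089 + 0.0438) = 1.8 for h = 5.
- Events to 12 months for h = 3: the steroid-arm risk is 1 − 0.9^(427/365) = 11.6%, so 35 × (0.100 + 0.116) = 7.6.
- Risk difference for h = 3: 2.65 − 0.89 = 1.8 percentage points at day 31, and 11.6 − 10.0 = 1.6 at 12 months.
- Rough standard error at day 31: √[(0.0089·0.9911 + 0.0265·0.9735)/35] = 0.031, so a 95% interval reaches about 6 percentage points either side.

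**Step 5, power.** With that 10% flat background, a 1-month mid-p test at two-sided 0.05 has at most 1.3% power (h = 5), because it needs at least 5 events against 0. The 12-month test has about 4% to 8%, depending on the approximation. If instead the 1-month risks were 5% and 25%, with 10% later risk in both arms, the 1-month test would have about 67%, against 42% to 48% for the 12-month test.

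**The case against.** The strongest reply is that the protocol never says the infection model runs over 12 months or yields one hazard ratio as its only summary. A reader might infer that it does, but the 12-month horizon comes from other outcomes. Censoring rules, risk windows and time-varying effects are commonly settled in the statistical analysis plan, which was not at hand. This stands, and it is why the point is conditional. It does not remove the point: the protocol has already chosen the model class for an outcome where proportional hazards is implausible, and one hazard ratio over available follow-up is the natural reading.

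Second, a 12-month comparison as randomized is a legitimate time-averaged quantity with a valid null test. It is not a faulty estimate of the on-treatment effect, and making later infections secondary would be a debatable choice. This also stands, so the Cox analysis should stay.

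Third, infections also appear among the adverse events in Table 2, and the abstract announces analyses of adverse reactions. On-treatment infections may therefore be visible elsewhere. That softens the consequence, but neither place specifies a between-arm comparison for the treatment month.

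Fourth, with so few events, imprecision dominates whichever window is used. This is correct, and Step 5 shows that a shorter window brings no general gain in power.

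**Conclusion.** The concern holds in conditional form. If one hazard ratio is fitted over 12 months, an excess confined to the 31-day course is diluted in every scenario examined: a true ratio of 3 appears as about 1.2 to 2.0, and 5 as about 1.3 to 3.1. This rests on assumed background rates, full follow-up and an excess ending with the course; carry-over lessens it.

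Some stronger conclusions are tempting but unsupported:
- That harm would be reported as almost no effect. This needs a roughly flat background hazard; if infections cluster soon after the stroke, the ratio stays clearly raised.
- That the Introduction singles out hospitalised infection as the feared harm. What it describes is concern about steroid effects on infectious mechanisms of the arteriopathy, such as varicella reactivation, not serious infection in general.
- That stroke recurrence needs the same change. It shares the Cox model, but the protocol gives no comparable reason to expect an effect limited to the treatment month, and none was quantified.

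**What to change.** In Statistical Analyses, keep the Cox regression for hospitalised infection and state the period it covers. Beside it, add the between-arm difference in cumulative risk from randomization to the 1-month visit, with a 95% confidence interval, and the same difference at 12 months. Use an interval method suited to very small counts. Name the day on which the first window closes: the data-monitoring section refers to a 30-day visit, one day short of a 31-day course. Add a sentence that a 12-month hazard ratio near 1 will not be read as absence of harm during treatment.

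The cost is protocol or analysis-plan wording and one more safety estimate. No extra visit is needed, provided that admissions for infection are recorded with their dates, as a time-to-event analysis already requires. The added estimate will have a wide interval and should be presented as such.
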